4.4 Assessment of bednet hanging and user perceptions by questionnaires

The head of the household or their representative will be asked to take part in completion of a questionnaire (**Appendix F**), to assess their perceptions of the nets provided, any difficulties encountered, and suggestions for improvements either to the nets or the way they are distributed. The sample size is based on that employed in an earlier pilot study of user perceptions conducted by the team in Kinshasa province. During the survey rounds, in all houses which have P3-BBnets the position of the barriers will be recorded by reference to a pictorial scale (**Appendix F**). Where bednets are hanging, observations will be made with the householder - if they consent - to check consistency with the reported hanging position.

4.5. Insecticide resistance quantification

Pyrethroid phenotypic resistance prevalence/ intensity and PBO synergy

WHO diagnostic dose bioassays will be used to characterise the resistance profile of the *Anopheles* vector community using assays with both deltamethrin alone (the pyrethroid on all nets distributed) and deltamethrin following prior exposure to the synergist PBO. Larvae will be collected from a range of habitats in public spaces and raised to adults in a field insectary. We propose to test 3 different concentrations (+ no insecticide controls) of deltamethrin with and without PBO, using standard WHO tube test procedures on adult mosquitoes (collected as larvae), each of which will be represented by 4 replicate tubes of N=25 female *Anopheles* + control tubes of N=25 females. The plan is shown below.

- Deltamethrin 1x (diagnostic dose)
- Deltamethrin 5x (if 1x does not kill ≥98%)
- Deltamethrin 10x (if 5x does not kill ≥98%)
- Deltamethrin 1x with PBO pre-exposure (if 1x alone does not kill ≥98%%)
- Deltamethrin 5x with PBO pre-exposure (if 5x alone does not kill ≥98%%)
- Deltamethrin 10x with PBO pre-exposure (if 10x alone does not kill 100%)

5. Data analysis

5.1 Epidemiological data

Data will be analysed as both intention to treat and per protocol, which may be important owing to the likely movement of ANC visitors to health centres not in their health area of residence, which will be recorded as part of ANC questionnaires. The primary outcome will be the prevalence of confirmed malaria from the ANC1 visitor surveys, which will be compared between treatment arms using either a generalized estimating equation or generalized linear mixed model with log link function. Covariables from ANC questionnaires may be incorporated into the models where significant. Owing to the difference in the physical appearance of nets, blinding of data collection is not possible but the study arms and health areas will be given random code numbers prior to analysis to facilitate blinding of statistical analysis.

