2.5. Cluster allocation and bednet distribution

Health areas from within the designated study health zones which have a functional ANC receiving on average ≥25 ANC1 visitors/month (based on DHIS2 data from September 2021-August 2022), form the list from which clusters were randomly-chosen. We will include all the health areas to which P3-BBnets are distributed as clusters for ANC1 monitoring and twice this number of PermaNet 3 clusters, chosen at random from within the same health zones.

Nine Lubumbashi health zones are identified (Fig. 6), which are wholly within Lubumbashi (this excludes Kipushi and Kafubu), and do not have military encampments (this excludes Kowe and Vangu). Within these nine health zones, health areas will by default receive PermaNet 3 unless randomly chosen to receive P3-BBnets. Table 1 shows the nine health zones including estimated projections of net need. In total, 133 health areas were identified (within the nine health zones)

which receive on average ≥25 ANC1 visitors per month and these were included in the list for allocation to be clusters in the study. Using a random number generator, 30 health areas were chosen, of which the first 21 were proposed for coverage by BBnets, with the additional health areas (random numbers 22-30 in order) serving as additions if sufficient P3-BBnets remain after distribution to the first 21, or as backups in case ANCs in any areas are no longer fully-functional or health centres do not wish to participate. The randomised choice was made by a non-study team member and was communicated to the SANRU distribution team.

Distribution of nets occurred under the standard procedures of the PNLP and SANRU distribution programme, which delivers bednets to health areas for distribution by community health workers. Based on the randomised allocation, each health area received bales of the appropriate bednet for onward distribution to households. Bednets are not routinely distributed with hanging materials, but for the P3-BBnets, string and hooks were provided (by the study team) to promote suspension of the barrier. Community health workers were trained to advise householders on the function of the barrier, its potential advantage and how to suspend it. If the householder decides not to suspend the barrier, the P3-BBnet will still provide protection in the same way as a PermaNet 3, given the identical physical and chemical composition of the net material.

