Figure 6. Map of Haut Katanga showing the 27 health areas. Inset shows enlargement within Lubumbashi city. Triangles show the nine health zones included for BBnet random allocation to health areas.

Table 1. Health zones (HZ) within Lubumbashi included in the list for inclusion, with information on the number of health areas and estimates for net need. The right column shows the random choices with the number of health areas that will be covered by Bbnets in the study, allowing for uncertainty in net need estimates. The final distribution list may differ slightly depending on logistical constraints

Possible HZ	Total HA (N=133)	HA (N=21)		
Kamalondo	2	0		
Kampemba	21	2		
Katuba	6	0		
Kenya	16	1		
Kisanga	15	0		
Lubumbashi	17	4		
Mumbunda	17	4		
Ruashi	25	6		
Tshamilemba	14	4		
Net need estimate				
lower	1704110	275531		
upper	1917124	309972		

Note added in V2.2: the final distribution was to 63 health areas as planned but these spanned 7 health zones rather than 9 (see Appendix G).

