2.5.1 Health area enrolment

It is planned that all health areas receiving P3-BBnets will be enrolled into the study. Twice the number of health areas that received PermaNet 3 within a specific health zone that is receiving P3-BBnets will be randomly chosen to be enrolled for monitoring in the study. Thus, for example in Kenya health zone (Table 1), which has one P3-BBnet area proposed for inclusion in the study, two PermaNet 3 health areas would be chosen at random from the remaining 15 for inclusion for monitoring. The final decision on PermaNet 3 health areas are chosen will be taken once the final report of the distribution of P3-BBnet locations is received from SANRU. Health centres will be contacted following liaison with the provincial health director followed by medical chiefs of each health zone for involvement in the study. The primary contact point for the study in each health centre will be the nurse responsible for running ante-natal clinics, who will be responsible for recruitment of visitors to the trial.

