Appendix G. Clusters to which nets were distributed

				Healt zones
cluster	ZDS	ADS	Net type	(where grouped)
				Ruashi-
1	Ruashi	Kijiba	BB nets	Kampemba Ruashi-
2	Ruashi	Kikunda	BB nets	Kampemba Ruashi-
3	Ruashi	Mukulu	BB nets	Kampemba
4	Ruashi	Kamasaka	BB nets	Kuashi- Kampemba
5	Ruashi	Kawama	BB nets	Kuashi- Kampemba
6	Ruashi	Kalukuluku	BB nets	Kuashi- Kampemba
7	Ruashi	Kizanga	BB nets	Ruashi- Kampemba Ruashi
Q	Ruashi	ا م //عالمم	BB nots	Kudsill- Kampemba
0 0	Lubumbashi	Tingi tingi	BB nots	Lubumbashi
10	Lubumbashi	Kacana 1	DD Hets	Lubumbashi
10	Lubumbashi	казара т	DD HELS	Lubumbashi Puachi
11	Kampemba	Safina	RR nots	Kampemba
TT	Kampemba	Sallia	DD HELS	Rupshi
12	Kampemba	Triangle	R B nets	Kampemba
12	Tshamilemha	Ciment Kat	BB nots	Tshamilemha
1/	Tshamilemba	Eoire	BB nots	Tshamilemba
14	Tshamilomba	Kigoma Quast	DD Hets	Tshamilemba
15	Konya		DD Hels	Konyo
10	Kenya	CASUP	BB nets	Kenya
1/	Kenya Nawa kuwa da		BB nets	Kenya Nawalawa da
18	Mumbunda	Plateau 1	BB nets	Mumbunda
19	Mumbunda	Maisha	BB nets	Mumbunda
20	Mumbunda	Salama	BB nets	Mumbunda
21	Kisanga	Wantanshi	BB nets	Kisanga Ruashi-
22	Ruashi	Baraka	P3 nets	Kampemba Ruashi-
23	Ruashi	Telecel	P3 nets	Kampemba Buashi-
24	Ruashi	Congo 2	P3 nets	Kampemba Ruashi-
25	Ruashi	Shindaika	P3 nets	Kampemba
26	Ruashi	Bendera	P3 nets	Kampemba Ruashi-
27	Ruashi	Congo 1	P3 nets	Kampemba Ruashi-
28	Ruashi	Luwowoshi	P3 nets	Kampemba
29	Ruashi	Neo Apostolique	P3 nets	Ruashi-

				Kampemba
				Ruashi-
30	Ruashi	Orphelinat	P3 nets	Kampemba Ruashi-
31	Ruashi	Orthodoxe	P3 nets	Kampemba
32	Lubumbashi	Kiwele	P3 nets	Lubumbashi
33	Lubumbashi	Gambela 2	P3 nets	Lubumbashi
34	Lubumbashi	Kalubwe 1	P3 nets	Lubumbashi
35	Lubumbashi	Kamatete	P3 nets	Lubumbashi Ruashi-
36	Kampemba	Cité de Jeunes	P3 nets	Kampemba Ruashi-
37	Kampemba	ECASET	P3 nets	Kampemba Ruashi-
38	Kampemba	Emmaûs	P3 nets	Kampemba Ruashi-
39	Kampemba	Kabanga	P3 nets	Kampemba Ruashi-
40	Kampemba	Kamasaka	P3 nets	Kampemba Ruashi-
41	Kampemba	Lapofa	P3 nets	Kampemba Ruashi-
42	Kampemba	Mubindu	P3 nets	Kampemba Ruashi-
43	Kampemba	Njanja	P3 nets	Kampemba Ruashi-
44	Kampemba	Sab	P3 nets	Kampemba Ruashi-
45	Kampemba	Suzanella	P3 nets	Kampemba
46	Tshamilemba	Hewa Bora 2	P3 nets	Tshamilemba
47	Tshamilemba	Rail	P3 nets	Tshamilemba
48	Tshamilemba	Agetraf	P3 nets	Tshamilemba
49	Tshamilemba	Kigoma Est	P3 nets	Tshamilemba
50	Tshamilemba	Kinsense Quartier	P3 nets	Tshamilemba
51	Tshamilemba	Industriel	P3 nets	Tshamilemba
52	Kenya	Lubumbashi	P3 nets	Kenya

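### The within-zone 2:1 rule was not met in Ruashi and Kampemba (30 of 63 clusters), and the primary model as described names no health-zone term to adjust for it

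*Protocol*

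**What the plan says.** **Selection of control clusters.** Protocol section 2.5 takes the PermaNet 3 monitoring clusters to be "chosen at random from within the same health zones" as the P3-BBnet clusters. Section 2.5.1 makes this a ratio inside each zone: "Twice the number of health areas that received PermaNet 3 within a specific health zone that is receiving P3-BBnets will be randomly chosen". Its worked example is Kenya zone, where one P3-BBnet area leads to two PermaNet 3 areas.

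**What happened.** The version 2.2 note under Table 1 reports that "the final distribution was to 63 health areas as planned but these spanned 7 health zones rather than 9" and refers to Appendix G. It does not mention a departure from 2:1 in any zone. Appendix G lists all 63 areas by zone and net type. Its last column, for zones "where grouped", labels every Ruashi and Kampemba area as one combined group. The protocol does not say what the grouping is for.

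**Analysis.** Section 5.1 has the primary outcome compared by a model family, "which will be compared between treatment arms using either a generalized estimating equation or generalized linear mixed model with log link function", and adds that "Covariables from ANC questionnaires may be incorporated into the models where significant". Neither health zone nor the combined group is named as a term.

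**The concern.** Controls were selected by zone, so the arms were meant to have the same zone mix, and an analysis that respects the selection would include zone. In the two zones that hold nearly half the clusters the mix differs by arm: the P3-BBnet arm leans towards Ruashi and the PermaNet 3 arm towards Kampemba. If malaria prevalence differs between these zones for reasons unrelated to the nets, part of that difference enters the estimated net effect. If Ruashi is the higher zone, the benefit of the barrier is understated; if Kampemba is, it is overstated. The trial is sized at about 80% power, so it has little room for a dilution of the effect. A zone term added once results are known would look post hoc, so it should be fixed beforehand.

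**Working it through.** **1. The plan's own sample size.** Inputs from section 2.4: 0.24 v 0.18, two-sided alpha 0.05, power 80%, 75 women per cluster, intraclass correlation 0.025, cluster ratio 0.5.
- Pooled proportion = (0.24 + 0.5 × 0.18)/1.5 = 0.22.
- Control-arm n without clustering = [1.96√(0.22 × 0.78 × 3) + 0.8416√(0.24 × 0.76 + 0.18 × 0.82/0.5)]² / 0.06² = 1,098.
- Design effect = 1 + 74 × 0.025 = 2.85.
- Clusters = 1,098 × 2.85/75 = 41.7, so 42, and half of that, 20.9, so 21. Power with 42 and 21 is 80.3%.

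The stated figures reproduce. The point does not touch the sample size.

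**2. Tally of Appendix G.**

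| Zone | BB | P3 | P3 under the 2.5.1 rule | Share of BB | Share of P3 | Difference |
|---|---|---|---|---|---|---|
| Ruashi | 8 | 10 | 16 | 0.381 | 0.238 | +0.143 |
| Kampemba | 2 | 10 | 4 | 0.095 | 0.238 | -0.143 |
| Lubumbashi | 2 | 4 | 4 | 0.095 | 0.095 | 0 |
| Tshamilemba | 3 | 6 | 6 | 0.143 | 0.143 | 0 |
| Kenya | 2 | 4 | 4 | 0.095 | 0.095 | 0 |
| Mumbunda | 3 | 6 | 6 | 0.143 | 0.143 | 0 |
| Kisanga | 1 | 2 | 2 | 0.048 | 0.048 | 0 |
| Total | 21 | 42 | 42 | | | |

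Ruashi and Kampemba hold 18 + 12 = 30 of 63 clusters (47.6%). Pooled, they are 10:20. Table 1 lists 25 eligible areas in Ruashi, so 25 - 8 = 17 were left, against the 16 the rule needs.

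**3. Bias without a zone term.** With equal cluster sizes, bias in the risk difference = sum over zones of (share of BB - share of P3) × zone prevalence. Only two zones contribute, so bias = 0.143 × (Ruashi - Kampemba prevalence). The gaps below are assumptions.

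| Gap (points) | Bias (points) | Share of the 6-point effect |
|---|---|---|
| 0 | 0 | 0% |
| 2 | 0.3 | 5% |
| 5 | 0.7 | 12% |
| 10 | 1.4 | 24% |

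The sign follows the gap. On the ratio scale of a log-link model with a true ratio of 0.18/0.24 = 0.75, the unadjusted ratio is 0.75 × (1 + 0.143 × gap/0.24). A gap of +10 points gives 0.75 × (1 + 0.0143/0.24) = 0.795, and -10 points gives 0.705. The planned 25% reduction would then read as about 20% or 30%.

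**4. The combined group does not help.** Inside the group, Ruashi makes up 8/10 of BB and 10/20 of P3 clusters, a difference of 0.30. The group's weight in a six-level adjusted estimate is (10 × 20/30)/14 = 0.476. The product is 0.30 × 0.476 = 0.143, the same bias as with no adjustment.

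**5. Error rates.** Cluster-level simulation of the Appendix G layout: cluster coefficient of variation 0.30, 75 women per cluster, 0.24 v 0.18, 6,000 runs per case, with the zone gap added on top of that variation.

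| Ruashi minus Kampemba (assumed) | No zone term: type I error / power | Six-level group | Seven-level zone |
|---|---|---|---|
| 0 | 5.4% / 79% | 5.4% / 79% | 5.2% / 78% |
| +5 points | 6.0% / 69% | 5.9% / 69% | 5.2% / 78% |
| +10 points | 8.0% / 54% | 7.9% / 53% | 5.4% / 80% |
| -10 points | 6.5% / 89% | 6.3% / 89% | 4.2% / 74% |

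The 89% in the last row is not a gain: it comes from an overstated effect.

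**6. Price of adjusting.** At equal residual variance, information is proportional to the sum of n₁n₂/(n₁ + n₂) over zones: 4.44 + 1.67 + 1.33 + 2.00 + 1.33 + 2.00 + 0.67 = 13.44. Without zones it is 21 × 42/63 = 14.00. The loss is 1 - 13.44/14.00 = 4%.

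**The case against.** **The model statement is brief, and its silence proves little.** Section 5.1 names a model family, does not list fixed or random effects, and excludes nothing. Adjustment terms are commonly left to a statistical analysis plan, and none is shown. This stands: one can say only that the protocol text names no zone term, not that the analysis will lack one. The mismatch between section 2.5.1 and Appendix G lies within the protocol and does not depend on that plan.

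**The imbalance is limited and looks like chance.** A reader might infer that zone is confounded with arm throughout. The documents do not support that: both arms occur in all seven zones, five are exactly balanced, and the seven-zone chi-square is 2.5 on 6 degrees of freedom (p = 0.87; Fisher p = 0.24 for Ruashi against Kampemba). Nor do the counts suggest a faulty draw. With Table 1's eligible areas, 25 - 8 = 17 remain in Ruashi and 21 - 2 = 19 in Kampemba, so 20 controls drawn from the pooled 36 would include 20 × 17/36 = 9.4 from Ruashi on average, against 10 observed. All of this stands. A non-significant imbalance still biases the estimate if the zones differ, because the bias depends on the size of the imbalance and the gap, not on a p-value.

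**The harm is conditional.** No zone prevalences are given. A 10-point gap exceeds the planned between-cluster standard deviation of 0.30 × 0.24 = 7.2 points. At 2 points the type I error stays at about 5%, with power about 75% unadjusted against 78% adjusted. This stands too, and is why the range is shown.

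**The grouping is disclosed, and 2:1 holds within it.** True, but the group is not the unit in section 2.5.1, and step 4 shows that adjusting for it removes none of the bias.

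**Conclusion.** The concern holds as a partial association between zone and arm that the protocol's analysis text does not address. The counts are certain, and they contradict section 2.5.1. The size is conditional: 0.143 times the Ruashi-Kampemba gap, so nothing if the two zones have equal prevalence and 1.4 points, 24% of the planned effect, if they differ by 10. It rests on equal cluster sizes and, for any figure above zero, on an assumed gap. A reader might go further and conclude that the primary comparison is invalid. The documents do not support this: zone can be adjusted for because both arms are present in every zone, no gap is documented, and a statistical analysis plan may already contain the term. It is a should-fix: a low-cost protection against a possible bias, together with a correction of the record.

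**What to change.** 1. **Section 5.1:** state that the primary model includes health zone as a fixed effect with seven levels, Ruashi and Kampemba separate, whatever its significance. Do not use the combined column of Appendix G for this. The coded data set given to the blinded analyst must carry a zone code. If a statistical analysis plan already has this term, refer to it.
2. **Section 2.5.1 and the note under Table 1:** state that 2:1 was met within each of five zones, but for Ruashi and Kampemba only in combination (8:10 and 2:10, together 10:20), and say what the grouping in Appendix G was for.

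**Cost:** a few sentences and no new data. The model gains six parameters on 63 clusters. If zones do not differ, this costs about 4% of information, or 1 to 3 points of power, in a trial planned at about 80%. The choice should be fixed before the arm codes are broken.

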A two-armed cluster randomised trial comparing PermaNet 3 with PermaNet 3-barrier bednets (P3-BBnets) is presented associated with a programmatic distribution of bednets in Haut Katanga province, southern DRC, which has taken place according to our specified distribution plan in May-June 2023. BBnets are identical to PermaNet 3 except for the addition of a longitudinal upright barrier, which contains the same ingredients (deltamethrin and PBO) as the roof of a PermaNet 3, and significantly enhances insecticide resistant mosquito killing capacity. The study will take place within health zones of the Lubumbashi area of Haut Katanga. Health areas within the health zones are randomised to receive the 300,000 P3-BBnets available, with all others receiving PermaNet 3. Training in hanging instructions for BBnets were provided to community health workers, who performed household distribution of all nets and additional hanging materials for the BBnets, which the trial team have supplied. The primary outcome variable for the study is prevalence of malaria recorded by routine testing of visitors at their first ante-natal clinics (ANC1), which provides an efficient and economical method for data collection. Visitors will be recruited by health centre staff to give their permission to take a rapid diagnostic test (RDT) for malaria and will be treated with artemisinin combination therapy (ACT) if positive; they will also be asked to complete a short questionnaire. All 21 health areas receiving P3-BBnets will be monitored for ANC1 malaria prevalence, as well as 42 areas receiving PermaNet 3. This design provides power to detect a 25% reduction in malaria prevalence attributable to P3-BBnets compared to PermaNet 3 as a reference. Data will be recorded over a continuous survey period of 3 months within the first year after distribution, during which surveys to characterise the malaria mosquito vector community and their insecticide resistance will also be performed, along with assessments of the hanging of bednets and questionnaires to assess user perceptions of the nets they have received. The physical and chemical integrity of nets, and their bioefficacy will also be assessed.

Funding and support

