Nets have been provided by Vestergaard and AMF. Funding for the trial is available from ERDF and UKRI-SIPF awards to LSTM. SANRU and the PNLP are providing support for the programmatic distribution. Ethical permission and sponsorship will be provided by LSTM, and ethical permission from University of Kinshasa.

Lay summary

Background

Performance of insecticide impregnated nets treated with pyrethroid insecticide is challenged by widespread pyrethroid resistance in *Anopheles* malaria vectors. New generation nets combine an additional insecticide or resistance-blocking molecule 'PBO' to combat resistance, but a more novel approach is to modify the physical design of the bednet to increase capacity to kill mosquitoes. LSTM have designed a patented barrier bednet, which adds an 40cm upright longitudinal section hanging above the roof of the bednet. The barrier intercepts mosquitoes during their typical flight paths when seeking to blood feed from sleepers under nets, increasing mosquito-net/insecticide contact. In partnership with the bednet producers, providers, distributors and malaria control programme bednets have been produced which are identical to the successful and widely distributed PermaNet 3, but with the added barrier, which incorporates both pyrethroid insecticide and PBO present on the roof of a PermaNet 3. In laboratory tests, these 'P3-BBnets' are shown to kill significantly more insecticide resistant mosquitoes than unmodified PermaNet 3, but the impact of P3-BBnets on malaria prevention has yet to be tested.

Overall Aim

The overall aim of the project is to evaluate the capacity of P3-BBnets to prevent malaria in comparison to unmodified PermaNet 3, in a cluster randomised trial as part of a programmatic distribution of bednets in Haut Katanga, Democratic Republic of Congo (DRC). Entomological surveillance will involve collections to characterise the *Anopheles* vector community and insecticide resistance profiles.

Methods in Brief

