2.4 Sample size

Projected sample size requirements for the number of clusters required were evaluated under two designs, the first with equal numbers of P3-BBnet and PermaNet 3 clusters monitored and the

second with a ratio of 0.5 (P3-Bbnet/ PermaNet 3), reflecting the more limited numbers of BBnets available. This second imbalanced design proved more feasible to provide suitable power and is presented. Calculations are applied with required power = 80%; type I error rate = 0.05; coefficient of variation for clustering of 0.30 (approximating that observed in the Sud Ubangi trial). We assume that 25 ANC1 visitors will be recruited on average per month per cluster. A single monitoring periods of 3 consecutive months is planned, giving an average cluster size of at least N=75.

Estimated numbers of clusters for a two-sample proportions test	Compute:	* Accepts numlist (
Cluster randomized design, Pearson's chi-squared test	Group-specific numbers of clusters	
Ho: p2 = p1 versus Ha: p2 != p1	Error probabilities	
	0.05 * Significance level	0.8 * Power ~
Study parameters:		
	Clusters	
alpha = 0.0500	Specify the ratio of the numbers of clusters:	Specify cluster sizes/sample sizes:
power = 0.8000	0.5 * Ratio, K2/K1	Group cluster size and ratio \sim
delta = -0.0000 (difference)		75
$p_1 = 0.2400$ $p_2 = 0.1800$		75 × Control ~
		1 * Ratio, M2/M1
Cluster design:	Allow fractional numbers of clusters and sample sizes	;
$k_{ratio} = 0.5000$	Effect size	
M1 = 75	Proportions	Report effect size as:
M2 = 75	0.24 * Control	Difference
rho = 0.0250		Difference
	0.18 * Experimental ~	0.025 * Intraclass correlation
Estimated numbers of clusters and sample sizes:		
V1 - 1 2	Specify varying cluster sizes	
$K_1 = 42$ $K_2 = 21$	* Coefficient of variation for clus	ter sizes
N1 = 3.150		
N2 = 1,575	Cide a	
	Sides:	
	Iwo-sided test	
	Treat number lists in starred(*) options as parallel	

Figure 5. Screenshot from Stata showing sample size calculation for the primary endpoint (malaria prevalence at ANC1s).

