The base malaria prevalence for Haut Katanga is taken from available malaria indicator survey (MICS) data (Fig. 2), which in Sud Ubangi corresponded closely with the ANC1 rate we observed in the PermaNet 2 arm. In the Sud Ubangi trial analysis, clusters receiving PermaNet 3 exhibited up to 30% lower prevalence than those receiving standard nets. This is assumed to represent the expected effect size for PermaNet 3, i.e. they will act to reduce malaria prevalence by 30% compared to the prevalence rate of 34% from the MICS (Fig. 2). Sample size calculations are based on a projected *additional* effect of P3-BBnets vs P3 of 25%. Therefore, the prevalence projected in each study arm is PermaNet 3 = 0.24 and BBnet = 0.18. The sample size calculation performed in Stata is shown in Fig. 5 and suggests that with these parameters 21 P3-BBnet clusters and 42 PermaNet 3 clusters are required.

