5.2 Household survey data

Quantitative data from surveys will be compared among areas (for BBnet barrier suspension) and time points (for BBnet barrier suspension, net durability assessments, and ordinal questionnaire data) using ANOVA, t-tests or non-parametric equivalents as appropriate. For qualitative data, coding will use Atlas.ti v9.

6. Data recording, management and confidentiality

The clinic nursing staff and assistants are familiar with the procedures involved, which are routine, and training will be provided to the appointed member of clinic staff who will be a part of the wider study team and responsible for ensuring the protocol is followed and data recording occurs correctly. The study team will be in contact via telephone with the study-associated member of the clinic staff to emphasise key points and answer queries. The DRC project PI will be responsible for coding the data so that data analysis will be performed blind to the identity of clusters by another member of the study team (at LSTM). Data will be entered into an Access database as soon as possible after data collection. All data collected will be anonymous, and GPS locations of individual houses will not be used in any report or presentation. Any photographs taken will only be taken of bednets and will not show residents.

7. Ethical considerations

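### Random arm codes cannot keep the primary analysis blind to arm, because 21 against 42 clusters shows which code is the P3-BBnet arm while the model and covariables are still open

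*Protocol*

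**What the plan says.** **Blinding.** Protocol section 5.1 says that nets look different, so data collection cannot be blinded, but "the study arms and health areas will be given random code numbers prior to analysis to facilitate blinding of statistical analysis". Section 6 makes the project lead in DRC responsible for "coding the data so that data analysis will be performed blind to the identity of clusters by another member of the study team". That team member sits at LSTM.

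**Allocation.** Section 2.4 plans an unequal design and concludes that "21 P3-BBnet clusters and 42 PermaNet 3 clusters are required". The opening summary repeats it: "All 21 health areas receiving P3-BBnets will be monitored for ANC1 malaria prevalence, as well as 42 areas receiving PermaNet 3". Appendix G lists the clusters by name and net type.

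**Model.** Section 5.1 compares the arms "using either a generalized estimating equation or generalized linear mixed model with log link function". It lets questionnaire covariables enter if they prove significant, and it plans both intention-to-treat and per-protocol analyses.

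**Questionnaire.** The antenatal form (Appendix E) holds the malaria test result (Q4.1). It also asks whether barrier nets were received (Q3.1), how the barrier hangs (Q3.2), and the village and health area of residence (Q1.4, Q1.6).

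**The concern.** A random code hides an arm only if nothing else in the file separates the coded groups. Here the groups differ in size by a factor of two, and the protocol says which is the smaller. An analyst handed arms A and B can name them from a one-line tabulation.

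This would matter little if every analytic choice were already fixed. Section 5.1, however, leaves open the choice between GEE and mixed model and the covariables to be kept. Blinding is the protection the protocol offers for those choices. If it fails, they can be made with the arm known and the treatment effect in view. What is at stake is the control of type I error and the credibility of a positive result.

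**Working it through.** **1. The plan's own cluster numbers.** Inputs from section 2.4: prevalences 0.24 and 0.18, two-sided alpha 0.05, power 80%, cluster ratio r = 0.5, 75 women per cluster, intraclass correlation 0.025.

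- Pooled prevalence = (0.24 + 0.5 × 0.18) / 1.5 = 0.22.
- Control women before clustering = [1.960 × √(0.22 × 0.78 × 3) + 0.842 × √(0.24 × 0.76 + 0.18 × 0.82 / 0.5)]² / 0.06² = 1,098 after rounding up.
- Design effect = 1 + 74 × 0.025 = 2.85.
- Control clusters = 1,098 × 2.85 / 75 = 41.7, rounded to 42. BBnet clusters = 20.9, rounded to 21.
- Power at 42 and 21 clusters = 80.3%.

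The plan's figures are reproduced. The imbalance is a fixed and published feature of the design.

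**2. The clusters as distributed.** Counting Appendix G by health zone:

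| Zone | BBnet | PermaNet 3 |
|---|---|---|
| Ruashi | 8 | 10 |
| Kampemba | 2 | 10 |
| Lubumbashi | 2 | 4 |
| Tshamilemba | 3 | 6 |
| Kenya | 2 | 4 |
| Mumbunda | 3 | 6 |
| Kisanga | 1 | 2 |
| Total | 21 | 42 |

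**3. What a two-level code reveals.** One code covers 21 clusters and the other 42. The smaller is the BBnet arm, with certainty and without any assumption. Counting women instead gives 21 × 75 = 1,575 against 42 × 75 = 3,150. With cluster sizes simulated at an assumed coefficient of variation of 0.3 to 0.8, the larger group was PermaNet 3 in at least 99.9% of runs.

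**4. The barrier items, if passed on.** Every woman is asked Q3.1; only those who answer yes go on to Q3.2. The protocol gives no expected answer rates. Assuming 40% to 90% yes in BBnet clusters and 2% to 20% in PermaNet 3 clusters, with 75 or 25 women per cluster, Q3.1 named the two coded arms correctly in all 4,000 runs of each scenario tried. Without any arm code, taking the 21 clusters with the most yes answers found 69% to 100% of the BBnet clusters. Withholding the arm code alone would therefore not be enough.

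**5. Type I error, as illustration only.** A null simulation used 4,000 runs, 63 clusters of 75, prevalence 0.24, intraclass correlation 0.025, four invented covariables modestly related to prevalence, and a cluster-level regression standing in for the mixed model. One fixed model rejected in 5.7% (GEE) or 4.8% (cluster-level regression) of runs. Keeping the smaller p-value of the two gave 6.6%. Keeping the smallest over two models and six covariable sets gave 12.7%. The covariable effects and the selection rule are assumptions; neither comes from the protocol.

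**The case against.** The strongest reply is that the protocol promises less than full arm blinding. Section 5.1 says only that the codes facilitate it, and section 6 speaks of the identity of clusters. The 2:1 ratio does not show which coded cluster is which health area. This stands in part: blinding to cluster names can survive if residence fields are coded too, so a reader who infers that the codes conceal nothing goes too far. But section 5.1 says that the arms themselves are coded for the purpose of blinding, and that part cannot work.

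A reader might also infer that the analyst's file holds the barrier items and residence text. The protocol does not say which fields the coder passes on. It only describes no step that removes them. Nor can village names be matched directly to Appendix G, which lists health zones and health areas, and the coding of health areas may be meant to cover the area of residence.

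A statistical analysis plan that is not shown may fix the model and covariables in advance. That would limit the harm, but it would not make an analysis on a two-level arm code blind to arm.

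Finally, a reader might draw an inference about the analyst from the fact that "LSTM have designed a patented barrier bednet". The protocol discloses this and separates coder from analyst. It makes a working safeguard more useful, but it is not evidence of an error.

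**Conclusion.** The point holds for blinding to arm. With 21 and 42 clusters, a two-level arm code identifies the arms with certainty, and this rests only on the protocol's own numbers. The further route through Q3.1 and Q3.2 is conditional on those fields reaching the analyst.

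The consequence is a risk: model and covariable choices left open in section 5.1 are not shielded from knowledge of arm. A reader might take the illustrative rejection rates of 6.6% and 12.7% as the size of the harm. The documents do not support that, because they do not say how the choice will be made or which covariables are candidates. Randomisation, outcome and sample size are unaffected. The wording should be changed, but the trial is not invalidated.

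**What to change.** Change section 5.1 and section 6 to a two-step release.

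1. The data coder issues a file without the arm code and without Q3.1 and Q3.2. Health area of clinic and of residence are replaced by random area codes, and village text is removed.
2. On this file the analyst fixes and dates the model type, covariables, analysis-set definitions and code.
3. The arm is then merged by area code and the locked code is run. Because residence is area-coded, the same merge gives the arm of the area of residence for the per-protocol set. A bare same-area or other-area flag could not do this, since it does not separate a move within an arm from a move between arms. The merge table must also cover residence areas outside the 63 clusters.
4. Barrier items are released afterwards for secondary analyses.

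If a dummy arm is needed to test code, use three coded groups of 21 clusters, two of them PermaNet 3. Splitting PermaNet 3 evenly within the grouped zones of Appendix G (Ruashi and Kampemba together: 10 BBnet and 20 PermaNet 3) gives every group 10, 2, 3, 2, 3 and 1 clusters, so neither size nor grouped zone reveals the arm. The separate Ruashi and Kampemba labels should then be left out, because 8 and 2 BBnet areas would stand against 5 and 5.

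If this is not wanted, state plainly that the analysis is not blind to arm.

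The cost is wording, a second data release and a short delay before barrier-use data reach the analyst. Design and sample size do not change.
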